13.2. Safety

“2.2 A list of the onset status of serious adverse events (Attachment Form 10)”

Patients for analysis: patients in the safety analysis group

Analysis objective: to show the onset status of serious adverse events

Analysis item: aggregate the following items per period for adverse events which occurred in the safety analysis period.

Calculate the number of patients and the percentage to the number of patients surveyed per number of sites surveyed, number of patients surveyed, number of patients with serious adverse events, number of serious adverse events, incidence of adverse events, incidence of serious adverse events and type of adverse reactions, etc. (SOC, PT).

Note: The classification of period should include at approval, cumulative and total.

Put * before the PT of unexpected events from “Precautions”.

“2.3 A list of target-patient summary (Attachment Form 3)”

Patients for analysis: patients whose survey form was locked

Analysis objective: to show a list of patients

Analysis item: provide the items for analysis and the definitions below.

(1) Case number

Provide a serial number starting 1 per patient.

(2) Name of site (company code)

Describe it in Japanese, as the official name. Obtain the name of site from “[CD Long-term]DCF code list_Company A.xlsx” and “[CD Long-term]DCF code list_Company E.xlsx”.

(3) Main establishing entity/code

Obtain the code from “Ultmarc re-examination classification”.

(4) Name of prefecture where the business is located

Fill in the name. Obtain the prefecture's name from “Ultmarc re-examination classification20150731.xlsx”.

(5) Patient abbreviation name

Fill in “not applicable” as mentioned in GB.

(6) Sex

Fill in man, women, unknown or not provided as mentioned in GB.

(7) Date of birth (or age)

Unify it in age. Fill in “A + age + “0000”” as mentioned in GB.

(8) Inpatient/outpatient

Fill in inpatient, outpatient, unknown or not provided as mentioned in GB.

(9) Indication

Code, name of disease: Obtain the MedDRA/J LLT code and LLT from the indication of Humira described in the survey form.

(10) Severity prior to administration

Note: Follow Time Allowance of “12.1 Assessment period for CDAI, WPAI, CRP to show CDAI when the administration was started at the following 4 levels:

<150: remission, ≥ 150 and <220 : mild, ≥ 220 and ≤ 450 : moderate, >450 : severe in severity

(11) Complications

Presence/absence: Refer to the “presence/absence of complications” defined in “10.1 General”.

Number of described complications: the number of PT codes encoded by MedDRA/J. If more than 1 identical PT code is found in a patient, count the PT as 1. Describe “0” for the case with no complications.

Term: Describe the PT of complication encoded by MedDRA/J. Arrange detailed classification of complication, the name of complication disease name, a serial number of the complication per patient. Leave the column blank for the case with no descriptions.

(12) Route of administration

Describe it as “SC”.

(13) Maximal dose (a dose)

The maximum of a dose Select the largest number in “administration status defined in “10.1 General” per patient.

(14) The mean dose (a dose)

The mean of a dose

It should be the value of “total dose/total dosing times” based on the “administration status (total dosing time, total dose)” defined in “10.1 General”.

(15) Unit

Use “MG”.

(16) daily dosing frequency (the maximum)

Use “1”.

(17) Period for administration

The value of “total dosing time” based on “ administration status (total dosing time, total dose)” defined in “10.1 General”.

(18) Concomitant medications

Drug code, the principal drug name: arrange concomitant medications for Crohn's disease (the concomitant medications checked at the indication: Crohn's disease in the survey form) per patient in the order of separate volume and description, and choose the concomitant medication data at the top. If there is no concomitant medication, leave the drug code column blank, and the name of the primary drug “null”.

Number of descriptions: count the number of the drug codes for concomitant medications arranged with the rule mentioned above. If more than 1 identical drug code is found in a patient, count it as 1 (for all the concomitant medications no matter whether the indication: Crohn's disease is checked). Describe “0” for the case with no concomitant medications.

(19) Effectiveness level

Follow Time Allowance of “12.1 Assessment period for CDAI, WPAI, CRP and no-intestinal conditions” to display remission/non-remission at the final assessment. Of note, if remission/non-remission at the final assessment is not reported, regard it as “unknown”.

(20) Adverse reactions

Handle the events with the identical PT code in a patient as 1 record regarding adverse events which occurred in the safety analysis period.

Organ-name code: select the SOC code. When presence/absence is “absence”, leave the column blank.

Adverse reaction code: select the PT code. When presence/absence is “absence”, leave the column blank.

Name of adverse reactions: select the PT. When presence/absence is “absence”, leave the column

blank.

Presence/absence: Select “present” for the data with both adverse events and causal relationship among the adverse reactions which occurred in the safety analysis period. If presence/absence of adverse events is unknown, select “unknown”. If presence/absence of adverse events is not provided, select “not provided”. Others are “absent”. If the reason is ‘safety assessment cannot be made’ in the patients excluded from the safety analysis, select “unknown”.

Number of descriptions: count the number of PT codes. If more than 1 identical PT code is found in a patient, count the PT as 1.

When presence/absence is “absence”, leave the column blank.

(21) Outcome

For PT codes displayed for adverse reactions, select the outcome with the highest priority in the “outcome” priorities defined in “10.2 Safety analysis”. When presence/absence of adverse reactions is “absence”, leave the column blank.

(22) Survey form number

Use the case number in this study.

(23) Dropout

If a patient is dropped out from both the safety analysis and the effectiveness analysis, display the case as “both_dropout”.

If a patient is dropped out only from the safety analysis, display the case as “Safe_dropout”.

If a patient is dropped out only from the effective analysis, display the case as “Effective_dropout”.

Note: If there are no applicable data in an aggregation column, display “0” and no columns should be left blank.

“2.4.1.1 A list of the onset status of adverse reactions (priority survey items)”

Patients for analysis: patients in the safety analysis group

Analysis objective: to show the summary statistics on the days to the onset as well as the number of patients per outcome and the days to the confirmed outcome (recovered or recovering) for adverse reactions of the priority survey items.

Analysis items: calculate the number of cases and the percentage to the number of patients in the analysis groups per type of adverse reactions (priority survey item, PT), and the number of patients with serious reactions and the percentage to the number of patients in the analysis groups regarding the adverse reactions which occurred in the safety analysis period. In addition, calculate the summary statistics (the number of patients, the mean, the minimum, the median, the maximum) for days to the onset per PT and priority survey item (for the total number of PTs) and for days from the onset date to the outcome (recovered or recovering) as well as the number of patients per outcome.

Note: When more than one identical PT is found in a patient, aggregate seriousness, days to the onset, outcome and days to the outcome (recovered or recovering) as 1 patient (case) in the following manner.

- Seriousness priority: serious > non-serious
- Days to the onset: identify the days as mentioned in “10.2 days from the first administration date of Humira to the adverse-event onset date”.
- Outcome: identify it as mentioned in “10.2 Outcome”.
- Days to outcome (recovered or recovering): identify the days as mentioned in 10.2 Days from an onset date of adverse events to the outcome confirmation date (recovered or recovering).

“2.4.1.2 A list of the onset status of adverse events (priority survey items)”

Patients for analysis: patients in the safety analysis group

Analysis objective: to show the summary statistics on the days to the onset as well as the number of patients per outcome and the days to the confirmed outcome (recovered or recovering) for adverse events of the priority survey items.

Analysis items: calculate the number of cases and the percentage to the number of patients in the analysis groups per type of adverse events (priority survey item, PT), and the number of patients with serious events and the percentage to the number of patients in the analysis groups regarding the adverse events which occurred in the safety analysis period. In addition, calculate the summary statistics (the number of patients, the mean, the minimum, the median, the maximum) for days to the onset per PT and priority survey item (for the total number of PTs) and for days from the onset date to the outcome (recovered or recovering) as well as the number of patients per outcome.

Note: When more than one identical PT is found in a patient, aggregate seriousness, days to the onset, outcome and days to the outcome (recovered or recovering) as 1 patient (case) in the following manner.

- Seriousness priority: serious > non-serious
- Days to the onset: identify the days as mentioned in “10.2 days from the first administration date of Humira to the adverse-event onset date”.
- Outcome: identify it as mentioned in “10.2 Outcome”.
- Days to outcome (recovered or recovering): identify the days as mentioned in 10.2 Days from an onset date of adverse events to the outcome confirmation date (recovered or recovering).

“2.4.2 A list of the onset status of the priority survey items per 100 patient-year”

Patients for analysis: patients in the safety analysis group

Analysis objective: to show the onset status of the priority survey items per 100 patient-year by adverse event, serious adverse event, adverse reaction, serious adverse reaction of patients in the safety analysis group.

Analysis items: calculate the number of patients and the percentage to the number of patients in the analysis groups per type of seriousness and type of priority survey items for adverse events/reactions which occurred between the first administration date of Humira and the final administration date of Humira + 28.

In addition, calculate the number of events/reactions and the event rate per 100 patient-year.

Note: Aggregate the total number of developed events/reactions including the overlapped ones which occurred in a patient.

“2.5.1 A list of the onset status of adverse reactions with/without self-administration”

Patients for analysis: patients in the safety analysis group

Analysis objective: to show the onset status of adverse reactions with/without self-administration

Analysis item: aggregate the following items with/without self-administration for adverse reactions which occurred in the safety analysis period.

Calculate the number of patients and the percentage to the number of patients surveyed per number of patients surveyed, number of patients with adverse reactions, etc. number of adverse reactions, type of adverse reactions, etc. (SOC, PT).

“2.5.2 A list of the onset status of adverse reactions with/without self-administration”

Patients for analysis: patients excluded from the safety analysis group

Analysis objective: to show the onset status of adverse reactions with/without self-administration

Analysis item: aggregate the following items with/without self-administration for adverse reactions which occurred in the safety analysis period.

Calculate the number of patients and the percentage to the number of patients surveyed per number of patients surveyed, number of patients with adverse reactions, etc. number of adverse reactions, type of adverse reactions, etc. (SOC, PT).

“2.6 Incidence of adverse reactions per onset period (serious)”

Patients for analysis: patients in the safety analysis group

Analysis objective: to show the onset status of serious adverse reactions per the onset period.

Analysis item: aggregate the following items by period for adverse reactions which occurred in the safety analysis period.

Calculate the number of patients and the percentage to the number of patients surveyed per number of patients surveyed, number of patients with serious adverse reactions, etc. number of serious adverse reactions, type of adverse reactions, etc. (SOC, PT).

Note: Aggregate the initial reactions among the identical PTs in a patient. Aggregate the events based on the segments which contain the initial onset period of adverse reactions among Time Allowance

defined in “12.4 Assessment period for the onset status of adverse reactions”. When calculating the number of patients with the target reactions, remove overlapped data per case number and onset period. When calculating the number of SOC, remove the overlapped data per case number, onset period and SOC.

Count the number of target patients and reactions by using the dates defined below until the assessment period applicable to Time Allowance defined in “12.4 Assessment period for the onset status of adverse reactions”.

- Discontinued patients: the final administration date of Humira + 28 days
- Not discontinued patients: the first administration date of Humira + 1120 days

Even if there is one adverse reaction, it should be counted as one patient in every period when the reaction persisted.

“2.7 Incidence of adverse reactions per set period”

Patients for analysis: patients in the safety analysis group

Analysis objective: to show the onset status of adverse reactions per onset period.

Analysis item: aggregate the following items by period for adverse reactions which occurred in the safety analysis period.

Calculate the number of patients and the percentage to the number of patients surveyed per number of patients surveyed, number of patients with adverse reactions, etc. number of adverse reactions, type of adverse reactions, etc. (SOC, PT).

Note: Aggregate the initial reactions among the identical PTs in a patient. Aggregate the events based on the segments which contain the initial onset period of adverse reactions among Time Allowance defined in “12.4 Assessment period for the onset status of adverse reactions”. When calculating the number of patients with the target reactions, remove overlapped data per case number and onset period. When calculating the number of SOC, remove the overlapped data per case number, onset period and SOC.

Count the number of target patients and reactions by using the dates defined below until the assessment period applicable to Time Allowance defined in “12.4 Assessment period for the onset status of adverse reactions”.

- Discontinued patients: the final administration date of Humira + 28 days
- Not discontinued patients: the first administration date of Humira + 1120 days

Even if there is one adverse reaction, it should be counted as one patient in every period when the reaction persisted.

“2.9 Incidence of adverse reactions (serious adverse reactions/adverse reactions) per background factor”

Patients for analysis: patients in the safety analysis group

Analysis objective: to show the incidence of adverse reactions per patient background factor and analyze them.

Analysis items: calculate the number of all patients, the percentage to the number of patients with serious adverse reactions and all patients, the number of patients with adverse reactions and the percentage to number of all patients, the tests for adverse reactions (Fisher's exact test for nominal-scale factors and Man-Whitney's u test for ordinal-scale factors) per the following patient background factor regarding the adverse reactions which occurred in the safety analysis period. Note that the test does not include the patients "with treatment history with anti-TNF α drug for Crohn's disease".

Note: the patient background factors are as follows:

Sex, age (year), body weight (kg), BMI (kg/m²), duration of illness (year), indication (registration form), allergy history, smoking history, with smoking history (details), self-administration, tuberculosis test status, hepatitis B virus test status (registration form), complication, complication: liver disorder, complication: renal disorder, complication: blood disorder, complication: respiratory disorder, complication: diabetes mellitus, complication: osteoporosis, complication: malignant tumour, medical history, medical history: tuberculosis, medical history: non-tuberculous mycobacteriosis, medical history: interstitial pneumonia, medical history: bronchitis bacterial, medical history: aplastic anaemia, medical history: pancytopenia, medical history: malignant tumour, prior medication for Crohn's disease, prior medication: anti-TNF α drug, prior medication: aminosalicylic acid drug, prior medication: corticosteroids, prior medication: immunosuppressant, prior medication: antibiotics, prior treatment for Crohn's disease, prior treatment: surgery, prior treatment: GCAP, prior treatment: enteral nutrition therapy, prior treatment: intravenous nutrition therapy, treatment history with anti-TNF α drug for Crohn's disease, with treatment history with anti-TNF α drug for Crohn's disease, concomitant medication, concomitant medication: aminosalicylic acid drug, concomitant medication: corticosteroids, concomitant medication: immunosuppressant, concomitant medication: antibiotics, concomitant therapy for Crohn's disease, concomitant therapy: surgery, concomitant therapy: GCAP, concomitant therapy: enteral nutrition therapy, concomitant therapy: intravenous nutrition therapy, site of disease: anus/perianal region, site of disease: rectum, site of disease: stomach/duodenum, site of disease: colon, site of disease: jejunum/ileum, intestinal complication, non-intestinal complication, work condition, CDAI when the administration was started, CRP

"2.9.xx Incidence of adverse reactions per background factor and seriousness"

Patients for analysis: patients in the safety analysis group

Analysis objective: to show the onset status of non-serious/serious adverse reactions per statistically-significant background factor based on the test results in 2.9.

Analysis item: aggregate the following items per background factor and seriousness for adverse reactions which occurred in the safety analysis period.

Calculate the number of patients and the percentage to the number of patients surveyed per number of patients surveyed, number of patients with adverse reactions, incidence of the reactions, number of adverse reactions and type of adverse reactions (SOC, PT).

“2.13.1 Incidence of adverse reactions with/without hepatic function disorder and per seriousness”

Patients for analysis: patients in the safety analysis group

Analysis objective: to show the onset status of non-serious/serious adverse reactions with/without hepatic function disorder

Analysis item: aggregate the following items with/without hepatic function disorder per seriousness regarding the adverse reactions which occurred in the safety analysis period.

Calculate the number of patients and the percentage to the number of patients surveyed per number of patients surveyed, number of patients with adverse reactions, incidence of the reactions, number of adverse reactions and type of adverse reactions (SOC, PT).

Note: Aggregate the most serious reaction among the identical PTs in a patient.

When calculating the number of patients with the target reactions, remove overlapped data per case number and seriousness. When calculating the number per SOC, remove the overlapped data per case number, seriousness and SOC.

“2.14.1 Incidence of adverse reactions with/without renal impairment and per seriousness”

Patients for analysis: patients in the safety analysis group

Analysis objective: to show the onset status of non-serious/serious adverse reactions with/without renal impairment

Analysis items: aggregate the following items with/without renal impairment per seriousness regarding the adverse reactions which occurred in the safety analysis period.

Calculate the number of patients and the percentage to the number of patients surveyed per number of patients surveyed, number of patients with adverse reactions, incidence of the reactions, number of adverse reactions and type of adverse reactions (SOC, PT).

Note: refer to the note of “2.13.1 Incidence of adverse reactions with/without hepatic function disorder and per seriousness”.

“2.15.1 Incidence of adverse reactions per seriousness in pediatrics and non-pediatrics”

Patients for analysis: patients in the safety analysis group

Analysis objective: to separately show the onset status of serious or non-serious adverse reactions in pediatrics and non-pediatrics.

Analysis items: aggregate the following items per seriousness in pediatrics and non-pediatrics

regarding adverse reactions which occurred in the safety analysis period.

Calculate the number of patients and the percentage to the number of patients surveyed per number of patients surveyed, number of patients with adverse reactions, incidence of the reactions, number of adverse reactions and type of adverse reactions (SOC, PT).

Note: refer to the note of “2.13.1 Incidence of adverse reactions with/without hepatic function disorder and per seriousness”.

“2.16.1 Incidence of adverse reactions per seriousness in the elderly and non-elderly patients”

Patients for analysis: patients in the safety analysis group

Analysis objective: to show the onset status of non-serious/serious adverse reactions in the elderly and non-elderly patients.

Analysis items: aggregate the following items per seriousness in the elderly and non-elderly patients regarding adverse reactions which occurred in the safety analysis period.

Calculate the number of patients and the percentage to the number of patients surveyed per number of patients surveyed, number of patients with adverse reactions, incidence of the reactions, number of adverse reactions and type of adverse reactions (SOC, PT).

Note: refer to the note of “2.13.1 Incidence of adverse reactions with/without hepatic function disorder and per seriousness”.

“2.17.1 A list of the onset status of adverse reactions/infections in this survey”

Patients for analysis: patients in the safety analysis group

Analysis objective: to show the onset status of adverse reactions and serious adverse reactions.

Analysis item: aggregate adverse reactions and serious adverse reactions regarding the following items based on the adverse reactions which occurred in the safety analysis period.

Calculate the number of patients and the percentage to the number of patients surveyed per number of patients surveyed, number of patients with adverse reactions, etc. number of adverse reactions, incidence of adverse reactions, etc., and type of adverse reactions, etc. (SOC, PT).

Note: refer to the note of “2.13.1 Incidence of adverse reactions with/without hepatic function disorder and per seriousness” for serious adverse reactions.

Put * before the PT of unexpected events from “Precautions”.

“2.17.2 A list of the onset status of adverse reactions/infections not in the follow-up period”

Patients for analysis: patients whose survey form was locked

Analysis objective: to show the onset status of adverse reactions and serious adverse reactions which occurred not in the follow-up period.

Analysis item: aggregate adverse reactions and serious adverse reactions regarding the following

items based on the adverse reactions which occurred not in the safety analysis period.

Calculate the number of patients and the percentage to the number of patients surveyed per number of patients surveyed, number of patients with adverse reactions, etc. number of adverse reactions, incidence of adverse reactions, etc., and type of adverse reactions, etc. (SOC, PT).

Note: refer to the note of “2.13.1 Incidence of adverse reactions with/without hepatic function disorder and per seriousness” for serious adverse reactions.

Put * before the PT of unexpected events from “Precautions”.

“2.17.3 A list of the onset status of adverse reactions/infections in this survey (patients excluded from the safety analysis)”

Patients for analysis: patients excluded from the safety analysis group

Analysis objective: to show the onset status of adverse reactions and serious adverse reactions.

Analysis item: aggregate adverse reactions and serious adverse reactions regarding the following items based on the adverse reactions which occurred in the safety analysis period.

Calculate the number of patients and the percentage to the number of patients surveyed per number of patients surveyed, number of patients with adverse reactions, etc. number of adverse reactions, incidence of adverse reactions, etc., and type of adverse reactions, etc. (SOC, PT).

Note: refer to the note of “2.13.1 Incidence of adverse reactions with/without hepatic function disorder and per seriousness” for serious adverse reactions.

Put * before the PT of unexpected events from “Precautions”.

“2.19 A list of the onset status of adverse events in this survey”

Patients for analysis: patients in the safety analysis group

Analysis objective: to show the onset status of adverse events, serious adverse events and non-serious adverse events.

Analysis items: aggregate adverse events, serious adverse events and non-serious adverse events regarding the following items among adverse events which occurred in the safety analysis period.

Calculate the number of patients and the percentage to the number of patients surveyed per number of patients surveyed, number of patients with adverse reactions, number of adverse reactions, incidence of the reactions, type of adverse events (SOC, PT).

Note: refer to the note of “2.13.1 Incidence of adverse reactions with/without hepatic function disorder and per seriousness” for serious adverse events.

“2.20 A list of the onset status of adverse reactions (all cases)”

Patients for analysis: patients in the safety analysis group

Analysis objective: to show the summary statistics on the days to the onset as well as the number of

patients per outcome and the days to the confirmed outcome (recovered or recovering) for adverse reactions.

Analysis items: calculate the number of cases and the percentage to the number of patients in the analysis groups per type of adverse reactions (SOC, PT), the number of patients with non-serious reactions and the percentage to the number of patients in the analysis groups, and the number of patients with serious reactions and the percentage to the number of patients in the analysis groups for the adverse reactions which occurred in the safety analysis period. In addition, calculate the summary statistics (the number of patients, the mean, the minimum, the median, the maximum) for days to the onset per PT, the number of patients per period from the onset date to the outcome (recovered or recovering), and the number of patients per outcome.

Note: When more than one identical PT is found in a patient, aggregate seriousness, days to the onset, outcome and days to the outcome (recovered or recovering) as 1 patient (case) in the following manner.

- Seriousness priority: serious > non-serious
- Days to the onset: identify the days as mentioned in “10.2 days from the first administration date of Humira to the adverse-event onset date”.
- Outcome: identify it as specified in 10.2 Outcomes of adverse events
- Days to outcome (recovered or recovering): identify the days as mentioned in 10.2 Days from an onset date of adverse events to the outcome confirmation date (recovered or recovering).

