12.4. Assessment period for the onset status of adverse reactions

Time allowance of assessment period with the first administration date of Humira as 1 is as follows:

Assessment period	Time Allowance(Day)
the first administration to Week 4 of administration	1-28
after Week 4 of administration to Month 3 of administration	29-84
after Month 3 of administration to Month 6 of administration	85-182
after Month 6 of administration to Year 1 of administration	183-364
after Year 1 of administration to Year 1 and Month 6 of administration	365-546
after Year 1 and Month 6 of administration to Year 2 of administration	547-728

Assessment period	Time Allowance(Day)
after Year 2 of administration to Year 2 and Month 6 of administration	729-910
after Year 2 and Month 6 of administration to Year 3 of administration	911-1092
Year 3 of administration -	1093 -

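### Charts 2.6 and 2.7 carry two incompatible rules for the period in which a reaction is counted; applied to the numerator, the second turns incidence by onset period into period prevalence

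*SAP*

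**What the plan says.** Both charts are titled as incidence tables. Their objectives are "Analysis objective: to show the onset status of serious adverse reactions per the onset period" (chart 2.6) and "Analysis objective: to show the onset status of adverse reactions per onset period" (chart 2.7). The periods are the nine windows of SAP 12.4, counted in days from first administration.

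The same note stands under both charts and has three parts:

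- **Onset rule.** "Aggregate the initial reactions among the identical PTs in a patient", followed by "Aggregate the events based on the segments which contain the initial onset period of adverse reactions among Time Allowance" of SAP 12.4. Patients are then de-duplicated by case number and onset period.
- **How far patients are followed.** Target patients and reactions are counted up to the window containing an end date. For one group this is "Discontinued patients: the final administration date of Humira + 28 days"; for patients who did not discontinue it is the first administration date plus 1120 days.
- **Persistence rule.** Of a single reaction, the note says that "it should be counted as one patient in every period when the reaction persisted".

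Neither note says which rule takes precedence, or that the persistence count is a separate row.

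**The concern.** The onset rule gives each patient and PT exactly one period. The persistence rule gives the same reaction between one and nine. Both cannot define the same cell.

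What is at stake is how these two charts read over time. Their use is to show whether new adverse reactions become more or less frequent over three years of treatment. If old, unresolved reactions are carried into later windows, a flat or falling onset rate can look flat or rising. If programmers instead choose one rule silently, the output rests on a decision that the SAP does not record.

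**Working it through.** **Inputs.** The SAP 12.4 windows are days 1–28, 29–84, 85–182, 183–364, 365–546, 547–728, 729–910, 911–1092 and 1093 onward. The notes stop counting at first administration + 1120 days, which is day 1121, so the last window is at most 1121 − 1093 + 1 = 29 days long. The five windows from day 183 to day 1092 are 182 days each.

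**Step 1: one reaction under each rule.**

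| Reaction | Onset rule | Persistence rule |
|---|---|---|
| Onset day 20, resolved day 400 | 1 period | 5 periods (1–28, 29–84, 85–182, 183–364, 365–546) |
| Onset day 20, never resolved, patient followed to day 1121 | 1 period | 9 periods |

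**Step 2: what follows in general.** The onset period is always one of the periods in which the reaction is present. The persistence count in a period is therefore the new onsets plus any patients carried over who are not already counted there. It is never below the onset count. It equals the onset count in days 1–28, because no post-dose reaction can be carried into that window. It can exceed it in every later window. That is period prevalence, and its sum over periods can exceed the number of reactions.

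**Step 3: can the persistence rule be run?** SAP 10.2 derives time from onset to outcome only for recovered or recovering outcomes with complete dates. Not recovered and unknown are also listed outcomes, and no end date is defined for them. Where a PT recurs, that derivation takes the longest episode, whereas the onset rule takes the first. A programmer would have to invent an end date for exactly the reactions that carry furthest.

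**Step 4: size.** The plan gives no figure for these charts and no reaction rates or durations, so there is nothing to reproduce. All figures below rest on assumptions: 200,000 simulated patients, at most one reaction each, constant onset hazard of 10% per 364-day year, exponential duration, follow-up to day 1121, no dropout. The denominator is the same under both rules, so the ratio of percentages is the ratio of counts.

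Ratio of the persistence percentage to the onset-only percentage:

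| Assumed median duration | 1–28 | 29–84 | 183–364 | 911–1092 | 1093–1121 |
|---|---|---|---|---|---|
| 7 days | 1.00 | 1.17 | 1.06 | 1.05 | 1.32 |
| 14 days | 1.00 | 1.28 | 1.12 | 1.11 | 1.66 |
| 60 days | 1.00 | 1.42 | 1.44 | 1.50 | 4.09 |
| 180 days | 1.00 | 1.50 | 1.74 | 2.56 | 10.76 |
| 14 days, 10% never resolve | 1.00 | 1.30 | 1.20 | 1.68 | 6.16 |
| 14 days, 30% never resolve | 1.00 | 1.34 | 1.40 | 2.81 | 14.3 |

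With 20% dropout per year the ratios for days 911–1092 are similar: 1.05, 1.12, 1.52, 2.59, 1.71 and 3.01.

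A hand check for the shorter durations: once onsets and resolutions balance, the ratio is about 1 + m/L, where m is mean duration (median / ln 2) and L is window length. For a 7-day median, m = 7/0.693 = 10.1 and 1 + 10.1/182 = 1.06. For 14 days, m = 20.2 and 1 + 20.2/182 = 1.11. For 14 days in the 29-day window, 1 + 20.2/29 = 1.70. These agree with the simulation.

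**Step 5: effect on the apparent trend.** With 30% never resolving, the onset-only percentage falls from 4.79% (days 183–364) to 3.97% (days 911–1092). The persistence percentage rises from 6.68% to 11.16% over the same windows. The rise comes from the counting rule alone.

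**The case against.** The strongest reply is that the last sentence was meant for the denominator. It comes directly after the instruction on how far to carry target patients across periods and after the two end dates. The translation is rough elsewhere: chart 2.7's title and its objective name the period differently. A garbled statement that each patient counts once in every period reached is plausible. This cannot be excluded. But the words speak of the reaction lasting, not of the patient being observed, so the sentence needs rewriting on that reading too.

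A second reply is that the rest of the note (objective, first reaction, onset segment, de-duplication) points to onset counting, and a programmer who follows it produces a correct incidence table. That is right, and it limits the claim. A reader might infer that the charts will in fact report prevalence. The documents do not support that: they show a conflict, and the inflation arises only if the persistence sentence governs the numerator.

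Third, the charts are descriptive, with no test or decision rule attached. Neither protocol section 9 nor SAP 5.1 names a by-period incidence analysis. Charts 2.4.1.1, 2.4.1.2, 2.4.2, 2.17.1, 2.19 and 2.20 do not carry the sentence. Priority-item rates, overall incidence and days to onset therefore survive either reading. This stands, and it lowers the weight of the point.

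**Conclusion.** The notes to charts 2.6 and 2.7 are internally contradictory, and nothing elsewhere in the SAP resolves it. Taken literally for the numerator, the closing sentence contradicts the titles and objectives and produces period prevalence in every period after days 1–28.

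The size is conditional. Under the stated assumptions, days 911–1092 are overstated by about 5% (7-day median) to 11% (14-day median), and by a factor of 2.56 to 2.81 for a 180-day median or 30% unresolved. The 29-day last window is distorted most. The simulation allows one reaction per patient. Where patients have several, de-duplication within a period would remove some of the carry-over from the patient-level rows.

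Two stronger inferences are tempting and fail. One is that only late-period risk is affected: days 29–84 are already raised (1.17 to 1.50). The other is that the survey's main safety results are biased: the outputs that carry them do not use this note. This should be corrected in the SAP, but it does not threaten the survey's principal findings.

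**What to change.** In both notes, delete the persistence sentence. Keep as numerator the patients whose first onset of the PT falls in the period, and as denominator the patients at risk in that period.

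If the sentence was meant for the denominator, replace it with: a patient counts as at risk once in every period reached up to the stated end date (final administration + 28 days if discontinued, first administration + 1120 days if not).

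If persistence is of interest, show it in a separate table labelled as period prevalence, with a defined end date for reactions not recovered or of unknown outcome.

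The cost is SAP wording in two notes. No new data are needed.
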